### 5.5.6 Follow-up to Adverse Events

All AEs occurring during or after the subject has discontinued the study are to be followed up until resolved or judged to be no longer clinically significant, or until they become chronic to the extent that they can be fully characterized.

If during AE follow-up, the AE progresses to an “SAE,” or if a subject experiences a new SAE, the investigator must immediately report the information to the sponsor/delegated CRO.

Even if the subject does not return to normal or to his or her previous state, the follow-up can be considered finished when the following procedures have been taken.

1. The investigator judges that the follow-up of the subject concerned is no longer necessary based on the progress made during the follow-up,
2. The reason for such a judgment is entered as a comment in the CRF for the follow-up, and
3. The sponsor judges that the reason is acceptable with regard to the safety of the subject concerned.

Refer to Appendix 6 “Liver Safety Monitoring and Assessment” for the details of follow-up of DILI (medical history, concomitant medications, history of alcohol intake and narcotic use).

### 5.5.7 Procedure in Case of Pregnancy

If a woman becomes pregnant or is proven to be pregnant during the study dosing period of within 28 days from end of treatment or early termination, the investigator should report the information to the sponsor or CRO in the same manner as for an SAE. The expected date of delivery, estimated fertility date, pregnancy result and neonatal data, etc., should be included in this information.

The investigator or other responsible personnel will handle the pregnancy in the same manner as an SAE and will follow the medical status of the mother, as well as the fetus, and report the outcome to the sponsor.

When the outcome of the pregnancy falls under the criteria for SAEs [spontaneous abortion, induced abortion, stillbirth, death of newborn, congenital anomaly (including anomaly in a miscarried fetus)] and when information on newborn falls under the criteria for SAEs

- CONFIDENTIAL -

(including death, congenital anomaly, and other, the investigator should respond in accordance with the report procedure for SAEs.

Additional information regarding the outcome of a pregnancy (which is categorized as an SAE) is mentioned below.

- “Spontaneous abortion” includes abortion and missed abortion.
- Death of a newborn within 1 month after birth should be reported as an SAE regardless of its relationship with the study drug
- If a newborn dies more than 1 month after the birth, it should be reported if a relationship between the death and intrauterine exposure to the study drug is judged as “possible” by the investigator or other responsible personnel
- In the case of a delivery of a living newborn, the “normality” of the newborn is evaluated at the birth.
- “Normality” of a miscarried fetus is evaluated by visual examination unless test results that indicate a congenital anomaly are obtained prior to miscarriage.

If a male subject impregnates his partner during the conduct of the clinical study, the subject should report the pregnancy to the investigator or other responsible personnel. The investigator must report the pregnancy to the sponsor or CRO.

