### 1.2.3 Toxicology

Nonclinical repeated-dose toxicity studies of ASP015K were conducted using rats (up to 26 weeks) and monkeys (up to 52 weeks). Toxicities observed in these studies were mainly related to gastrointestinal, hematopoietic, muscular, and immune systems. All these findings were reversible and resolved upon the withdrawal of ASP015K. Muscle toxicity was observed in monkeys: mild multifocal muscle necrosis in 1 female at 60 mg/kg per day in the 4-week preliminary study; elevation of CPK and LDH without histopathological change of the muscle in 2 males at 60 mg/kg per day in the 4-week preliminary study; elevation of CPK and LDH without histopathological changes in 1 male that was sacrificed in extremis in 13-week study, and a transient increase of CPK without histopathological changes observed in another male in the same 13-week study.

Genotoxicity studies were conducted *in vitro* and *in vivo*. ASP015K was negative in the reverse mutation test in bacteria but was positive in an *in vitro* chromosomal aberration test in Chinese hamster lung cells. ASP015K was negative in 2 *in vivo* genotoxicity studies, the unscheduled DNA synthesis test in rats and the micronucleus test in mice. These results suggested that ASP015K had little potential to induce chromosomal aberrations *in vivo*.

In toxicity studies on the fertility and early embryonic development in rats, the viability of embryos decreased after implantation and the number of live embryos decreased in the 100 mg/kg per day group compared with the control group. ASP015K neither induced general toxicity nor impacted male or female fertility up to the dose of 100 mg/kg/day. In an

- CONFIDENTIAL -

embryo–fetal development study in rats, increased incidences of skeletal abnormalities and variations and visceral variations were noted at 30 mg/kg/day and higher, while increased incidences of visceral and external abnormalities were observed at 300 mg/kg/day. NOAEL for embryo–fetal development in rats was 10 mg/kg/day. In an embryo–fetal developmental toxicity study in rabbits, no teratogenicity was observed; however, increased postimplantation loss and decreased numbers of live fetuses were noted at 10 mg/kg/day.

Four- and 13-week toxicity studies of ASP015K administered in combination with tacrolimus, MMF, or MTX demonstrated no significant synergistic toxicities in rats.

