### **5.1.6 Compliance Rules to be Observed by Subjects throughout the Study**

The investigator, sub-investigator, or collaborator will explain the following to the subjects during the study period.

- The subject should come to the study center on the day of each study visit without taking that day's dose of the study drug prior to the visit. The subject must also fast for at least 8 hours prior to the blood sampling at the time of the study visit. If need arises for the subject to visit the study center on an unscheduled day after taking that day's dose, for reasons such as AE, the subject should visit the study center regardless of whether and when the study drug and meal have been taken.
- If a new treatment (starting to take a new drug or use a new therapy, etc.) has been prescribed by another department or another medical institution during the study period, the subject should contact the investigator/sub-investigator before starting to use the new treatment, and follow the instructions given by the investigator/sub-investigator. If it is not possible to contact the investigator or sub-investigator in advance, the subject should contact one of them, or the collaborator, as soon as possible.
- Any subject who wishes to take a prescription medicine or over-the-counter drug unconfirmed by the investigator/sub-investigator should consult with the investigator/sub-investigator or collaborator in advance.
- Because the effects that the study drug may have upon pregnancy and the unborn child remain unclear, subjects should be certain to practice 2 or more methods of proper contraception that shall be used by male subjects throughout the study period and for 90 days after end of treatment, and by female subjects throughout the study period and for 60 days after end of treatment.

- CONFIDENTIAL -

- Female subjects must not nurse during the study period and for 60 days after the end of treatment.
- In principle, the subject will come to the study center for the study visits on the specified dates. If it is not possible to come on the specified date, the date of the visit will be adjusted to the nearest possible date.
- The subject should visit the study center without delay when instructed by the investigator or sub-investigator to do so because, for example, the laboratory testing has revealed CPK or liver function values to be in the range that requires CPK monitoring or liver function monitoring.

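### Required pregnancy reporting ends 28 days after treatment for women and at an undefined point for men's partners, against contraception periods of 60 and 90 days

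*Protocol*

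**What the plan says.** **Reporting duty (Protocol 5.5.7).** For a woman who becomes or is proven pregnant, the trigger period is "during the study dosing period of within 28 days from end of treatment or early termination, the investigator should report the information". Such a report goes to the sponsor or CRO and is handled like an SAE. It includes the delivery date, outcome and neonatal data, and mother and fetus are followed. For men the text reads: "If a male subject impregnates his partner during the conduct of the clinical study, the subject should report the pregnancy". This goes first to the investigator, who passes it on. No number of days after treatment is given for partners.

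**Contraception (Protocol 5.1.6).** The rule for women is that contraception applies "by female subjects throughout the study period and for 60 days after end of treatment". The period for men is longer, at 90 days. The stated reason begins: "Because the effects that the study drug may have upon pregnancy and the unborn child remain unclear". The eligibility criteria (synopsis and Section 3.3) repeat the 60 and 90 days for subjects from all three preceding studies. Their rationale there is only general considerations for clinical studies.

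**Last contact.** The follow-up visit falls 28 days after dosing ends, with a 7-day allowance either way, and takes place only if the investigator judges it necessary (Table 1 and notes d and e). Otherwise the end-of-treatment visit is the last one (Start and End of Study). AE collection stops at follow-up (Table 1, note q).

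**Analysis (SAP 7.5.6).** Pregnancies appear as a subject listing only.

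**The concern.** The protocol sets a post-treatment precaution period because effects on the unborn child are unknown, but its duty to report and follow a pregnancy stops earlier for women and at an unstated point for men's partners. A woman who conceives 35 days after end of treatment is still within her contraception period, yet no rule requires a report, outcome follow-up or neonatal data.

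There is a nonclinical reason to want such outcomes. Section 1.2.3 states that in rats "increased incidences of skeletal abnormalities and variations and visceral variations were noted at 30 mg/kg/day and higher", and reports post-implantation loss with fewer live fetuses in rabbits at 10 mg/kg/day. Human pregnancy data in this study can come only from unplanned cases. What is at stake is the completeness of the pregnancy listing; no efficacy endpoint or analysis is affected.

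**Working it through.** The plan derives no figure here, so the check sets the two windows against each other. Both are taken to start on the same day, end of treatment. The follow-up visit is timed from the last dose, which may differ by a day or two.

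**Inputs**
- Reporting, women: 28 days (5.5.7).
- Contraception: women 60 days, men 90 days (5.1.6; 3.3).
- Follow-up visit: day 28, allowable days 21 to 35 (Table 1; 7.8.1), optional.
- Study period: ends for a subject at the final protocol evaluation (List of Key Study Terms).
- End of study: the last subject's final assessment (Start and End of Study).

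**Women**

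Uncovered days = contraception period − reporting period = 60 − 28 = 32; 32/60 = 53%.

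**Men**

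| Reading of study conduct | Uncovered days | Share of 90 |
|---|---|---|
| Ends at subject's follow-up visit, day 35 | 90 − 35 = 55 | 61% |
| Same, day 28 | 90 − 28 = 62 | 69% |
| Same, day 21 | 90 − 21 = 69 | 77% |
| Follow-up not held; end-of-treatment visit is last | nearly 90 | nearly 100% |
| Ends when the whole trial ends | max(0, 90 − d) | 0% if d ≥ 90 |

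Here d is the number of days from the man's end of treatment to the last subject's final assessment. The protocol does not say which reading applies.

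**Does another rule close the gap?**
- AE collection does not go past follow-up.
- Section 5.5.6 follows AEs after a subject leaves and requires reporting of new SAEs. It does not require reporting of a pregnancy as such, and a partner is not a subject.
- The pregnancy test at follow-up is done only if the investigator decides it is needed (5.4.4).
- No section extends pregnancy reporting to day 60 or day 90.

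**How much exposure is likely in the gap?**

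Section 1.2.2.2 gives a mean single-dose half-life of 2.8 to 18.5 hours. At the longest value:
- 28 days = 28 × 24 / 18.5 ≈ 36 half-lives.
- 35 days = 35 × 24 / 18.5 ≈ 45 half-lives.

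On plasma figures, little parent drug remains when the 28 days end.

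**The case against.** The strongest reply is pharmacokinetic. After about 36 half-lives an embryo has negligible direct exposure, and the animal findings arose under dosing, not after washout. Section 1.2.3 also reports no effect on male fertility up to 100 mg/kg/day and negative in vivo genotoxicity tests. The informative time is dosing, which can last years, plus the first days after it; for women both are covered. The 28 days also match the last scheduled contact, and contraception and reporting windows may serve different purposes.

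Most of this stands, and it limits how the percentages may be read. A reader might infer that 53% of exposed pregnancies in women, or at least 62 of 90 days in men, go uncaptured. The documents support neither. The shares count days, not exposures. The value of 62 is not a lower bound, since a day-35 visit leaves 55 and a trial-level reading may leave none. The protocol nowhere calls 60 or 90 days a fetal-risk period; they are contraception periods.

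A reader might also infer that a woman's pregnancy conceived within 28 days but recognised later escapes. It does not: 5.5.7 covers becoming pregnant in the window as well as being proven pregnant in it. Nor does anything forbid a later voluntary report.

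What remains is that the sponsor chose 60 and 90 days for caution about the unborn child and gives no reason for a shorter or undefined reporting duty. Leaving late reports to chance after subjects have gone is weak collection of data the sponsor says it wants.

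**Conclusion.** The mismatch is real and modest. For women, 32 of 60 days of the contraception period carry no reporting duty; this follows directly from the text. For men, the firm finding is that the partner-reporting period is undefined. The gap is 55 to 69 of 90 days if it ends at the subject's follow-up visit, nearly all 90 if that visit is not held, and possibly none on a trial-level reading.

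Not captured means not required to be captured. The documents give no pregnancy rate, so no number of missed pregnancies can be stated, and late conceptions probably involve little direct exposure. The point is worth acting on because the change is cheap and makes outcome capture consistent with the protocol's own precaution.

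**What to change.** Reconcile 5.5.7 with 5.1.6 as follows:

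1. Require that a pregnancy conceived within the protocol's own contraception periods (60 days for female subjects, 90 days for partners of male subjects), counted from end of treatment as in 5.1.6, be reported and followed to outcome whenever it becomes known.
2. Replace the undefined study-conduct phrase for partners with that stated period after end of treatment.
3. Correct the garbled link between the dosing period and the 28 days in the women's sentence, where *of* appears to stand for *or*.
4. Have subjects told at the end-of-treatment visit to notify the site of such a pregnancy. The consent pages are not in the reviewed copy, so any existing instruction there should be checked first.

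The cost is a few sentences and a few extra pregnancy reports after subjects have left the study. No contraception rule, visit or test changes.

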### **5.5.8 Supply of New Information Affecting the Conduct of the Study**

In Japan:

1. When information is obtained regarding serious and unexpected adverse drug reactions (or other) that are specified in Article 80-2 Paragraph 6 and Article 273 of the Law for Ensuring the Quality, Efficacy, and Safety of Drugs and Medical Devices (or adverse drug reactions during the post-marketing clinical study), the sponsor should inform all the investigators involved in the clinical study, the head of the study center, and the regulatory authorities of such information.

Upon receiving such a report, the head of the study center will decide whether the clinical study should be continued after hearing the opinions of the IRB. The investigator will supply the new information to the subjects, in compliance with Section 8.2.3.2, Supply of New and Important Information Influencing the Subject’s Consent and Revision of the Written Information.

2. In addition to 1 above, the head of the study center should submit any reports received from the sponsor or investigator to the IRB regarding revision of the investigator’s brochure (This is not applicable during a post-marketing clinical study) or the protocol, revision of the written information, particulars related to the quality, efficacy, or safety of the study drug, important information on properly conducting the study, or other revision of materials for discussion by the IRB.

In Korea and Taiwan:

- CONFIDENTIAL -

When the sponsor gains new information suggesting adverse impact on the subjects' safety, safe conduct of the clinical study, or the IRB/IEC approval for study continuation, the sponsor will immediately notify all investigators, all study sites, and relevant regulatory authorities.

The sponsor must immediately report SAEs to all participating principal investigators, study sites (and the IRBs/IECs if appropriate) in compliance with local requirements and the relevant regulatory authorities.

When information necessary for conducting the clinical study properly (including "Dear Doctor Letters" but not limited to that) becomes available and leads to a protocol amendment, the sponsor should inform the regulatory authorities, as well as all investigators and medical institutions involved in the clinical study, who will then inform the IRB/IEC of such information, and when needed, should amend the Written Information.

### **5.5.9 Deviations from the Protocol and Other Actions Taken to Avoid Life-Threatening Risks to Subjects**

The investigator or other responsible personnel must not deviate from or amend the protocol, without obtaining prior written agreement with the sponsor and prior written approval based on the review by the IRB/IEC.

In Japan:

However, when the investigator does not follow the protocol for medically inevitable reason and in order to avoid urgent risks for subjects, the investigator should take the following actions:

1. Describe the content of the deviation or amendment and the reason for it in a written notice and immediately send the document stating the deviation or amendment and the reasons to the sponsor and the head of the study center. Keep a copy of the notice.
2. Consult with the sponsor at the earliest possibility for cases in which it is necessary to amend the protocol in order to avoid risk to the subjects. Obtain approval for a draft of the amended protocol from the IRB and the head of the study center as well as written agreement with the sponsor.

In Korea and Taiwan:

When the investigator does not follow the protocol in order to avoid urgent risks for subjects, the investigator should report to sponsor, IRB/IEC, and regulatory authority (if applicable) in compliance with local requirements.

## **5.6 Test Drug Concentration**

Not applicable.

- CONFIDENTIAL -

## **5.7 Other Measurements, Assessments, or Methods**

### **5.7.1 Pharmacodynamic Parameters**

For the assessment of pharmacodynamics, lymphocyte subset determination is performed in this study (Section 5.3.2, Pharmacodynamics Assessments).

Blood samples for the lymphocyte subset determination are drawn using 2 mL vacutainer tube containing EDTA-2K in Japan, and 3 mL vacutainer tube containing EDTA-2K in Korea and Taiwan. For the procedures of collection, storage, and dispatch of blood samples, refer to the explanation of test procedures supplied with the test kit.

## **5.8 Total Amount of Blood**

The total amount of blood drawn for samples will differ from subject to subject in this study because duration of participation in the study will differ depending upon the subject.

The volume of blood drawn per sample and the total annual sample volume are shown in the table below. In addition, blood samples are collected for ESR determination performed at each study center; the volume will differ from center to center (approximately 1 to 2 mL per sample). See Table 1, Schedule of Assessments, for details regarding the blood-sampling schedule.

Blood samples will be taken at other times as necessary to follow up on laboratory test values obtained.

- CONFIDENTIAL -

[Subjects who transferred from RAJ1]

Assessment	Volume of sample	Total annual sample volume (No. of draws)	
		First year	2nd year and later
Hematology	2 mL	28 mL (14 times)	8 mL (4 times)
Biochemistry (including CRP and lipid profile tests)	14 mL	196 mL (14 times)	56 mL (4 times)
Lymphocyte subsets	2 mL	4 mL (2 times)	2 mL (1 time)
Total	18 mL	228 mL	66 mL

[Subjects who transferred from RAJ3 or RAJ4]

Assessment	Volume of sample	Total annual sample volume (No. of draws)	
		First year	2nd year and later
Hematology	Japan: 2 mL Korea: 3 mL Taiwan: 3 mL	Japan: 10 mL (5 times) Korea: 15 mL (5 times) Taiwan: 15 mL (5 times)	Japan: 8 mL (4 times) Korea: 12 mL (4 times) Taiwan: 12 mL (4 times)
Biochemistry (including CRP and lipid profile tests)	Japan: 14 mL Korea: 15.5 mL Taiwan: 13.5 mL	Japan: 70 mL (5 times) Korea: 77.5 mL (5 times) Taiwan: 67.5 mL (5 times)	Japan: 56 mL (4 times) Korea: 62 mL (4 times) Taiwan: 54 mL (4 times)
Lymphocyte subsets	Japan: 2 mL Korea: 3 mL Taiwan: 3 mL	Japan: 4 mL (2 times) Korea: 6 mL (2 times) Taiwan: 6 mL (2 times)	Japan: 2 mL (1 time) Korea: 3 mL (1 time) Taiwan: 3 mL (1 time)
Total	Japan: 18 mL Korea: 21.5 mL Taiwan: 19.5 mL	Japan: 84 mL Korea: 98.5 mL Taiwan: 88.5 mL	Japan: 66 mL Korea: 77 mL Taiwan: 69 mL

\* Additional 5 mL of blood per sample needs to be drawn in Japan and Taiwan, and 8.5 mL in Korea at the scheduled visits after initiation of study drug administration if HBV-DNA assay is performed.

\* Additional 4 mL of blood per sample needs to be drawn in Japan, and 5 mL in Korea and Taiwan if determination of CK-MB, troponin T, and aldolase is performed.

## 6 TERMINATION OF THE CLINICAL STUDY

1. When the sponsor is aware of information on matters concerning the quality, efficacy, and safety of the study drugs, as well as other important information that may affect proper conduct of the clinical study, the sponsor may discontinue the clinical study and send a written notice of the discontinuation along with the reasons to the investigator [unique to Japan: and the head of the study center].

- CONFIDENTIAL -

2. If the investigator wishes to discontinue the study in the particular study center while the study is still in progress, the investigator should contact the sponsor [unique to Japan: and the head of the study center] immediately to inform them of the discontinuation and the reason for it.

## 7 STATISTICAL METHODOLOGY

A detailed elaboration of the statistical analysis will be included in a separate statistical analysis plan based on the opinions and advice from a medical expert. After review, it will be finalized prior to data lock. For the analyses of efficacy and pharmacodynamics variables in this extension study, values at the baseline in the previous studies (RAJ1, RAJ3, and RAJ4) will be used as the baseline values. However, changes from baseline values of this extension study will also be examined where appropriate. For the evaluation of safety, Week 0 of this extension study (015K-CL-RAJ2) will be referred to as the baseline; however, changes from baseline values of the previous studies (RAJ1, RAJ3, and RAJ4) will also be examined where appropriate.

